6.3 Final Study Contact

Contact 10, Infant Age 24 Months + 90 days

Infant health record review by blinded research coordinator to record clinical assessments through 2-year well-child check (up to 27 months of age). Coordinator to collect the following:

- Primary Endpoint: Provider diagnosis of AD or eczema
 - Any diagnosis of eczema, atopic dermatitis, or atopic eczema at any visit
 - Any qualifiers like “probable” or “probable.” These will be coded as having atopic dermatitis for the primary analyses.
 - Date of first diagnosis
 - Treatment(s) used for AD- dose, frequency
- Secondary Endpoints from chart review
 - Date of first diagnosis of AD by clinician in chart
 - Approximate date of onset of symptoms if recorded (age of child in months)
 - Presence of wheeze and date of onset
 - Diagnosis of atopic comorbidities: asthma, allergic rhinitis, food allergy
 - Any allergy testing- skin prick tests or blood
- Medication history: Any skin-directed prescription therapies:
 - Antibacterial (e.g. mupirocin, bacitracin)
 - Anti-inflammatory (topical corticosteroids, topical calcineurin inhibitors, crisaborole)
 - Antifungals (e.g. ketoconazole, econazole, terbinafine)
 - Antivirals (e.g. acyclovir ointment)
 - Any oral antibiotics prescribed for any indication- name of antibiotic, duration indicated on prescription, and indication if stated
- Provider diagnosis of hay fever/allergies, asthma, and/or food allergies
- Gestational age
- Birth weight
- Adverse events
 - Only skin product-related adverse events mentioned in the clinical chart will be captured. Event start and stop dates (if known) will be recorded, outcome and treatments needed.
 - Any serious adverse events (SAEs), not only skin-related, will be captured

- In infants who were diagnosed with AD/eczema:
 - Date of diagnosis
 - Severity
 - Prescribed medications for treatment of AD, eczema, or rash

6.4 Post-Participation Study Contact

After participation in the study surveys has concluded, parents will be asked about willingness to participate in additional research:

- Willingness to continue in the cohort or other research
 - Preferred contact method

6.5 Withdrawal Contact

If a dyad withdraws early parents will be asked to provide the following information:

- Reason for withdrawal
- Components of the study from which they will withdraw participation (e.g. intervention only, intervention plus continued data collection)

7 STUDY PROCEDURES /EVALUATIONS

Questionnaires and data abstracted from the infant's health record comprise the majority of study procedures. No in-person study procedures will take place, though infant/parent dyads will complete well-child visits with their provider during the first 2 years of life as part of standard clinical care. Appendix I and Appendix J provide a schedule of events with an overview of the study schedule and procedures.

7.1 Study Procedures/Evaluations

- Questionnaires: quantitative, parent-reported data will be collected from questionnaires. Parents will complete questionnaires about their infant's health, AD symptoms or diagnosis, allergy symptoms or diagnosis, AD risk or family history, and other measures listed in Appendix F.
- Validated AD instruments: validated instruments which measure AD symptoms, severity, risk-factors, and impact of AD on quality of life (Appendix A-E) will be used in the questionnaires.
- Medication history: only information about skin-related medications and antibiotic use will be collected from parents and from the infant medical record. These medications may include topical over-the-counter and/or prescribed medications, as well as oral medications that are used to treat skin conditions (i.e. antibiotics or steroids).
- Health record abstraction: a health record abstraction conducted at 12 months and the final study contact will collect data about provider-diagnosis of AD and allergies, treatment of AD and skin-related diseases, and severity of AD.

8 ADVERSE EVENTS REPORTING

Adverse events (AEs) in this study will be identified (1) by parent report through responses the parent provides in electronic contacts (refer to section 5.4), selecting the link for reporting skin product-related AEs provided on the websites, (2) by parent report via phone or email contact to the CCC, and (3) by review of the infants' medical record through ages 27 months. AEs will be graded as to their expectedness and attribution by the principal investigator (unrelated, possibly, probably or definitely related to the protocol). Due to the nature and low risk of the intervention, only skin product-related adverse events in randomized infants will be actively captured by patient report at least quarterly. These skin product-related AEs may qualify as serious adverse events (SAEs) or Unanticipated Problems (UPs) and will be actively monitored and reported by the PI and study team on a daily basis. All SAEs, not just skin product-related, will also be captured by patient report quarterly.

Clinic chart audits through 27 months will record all skin product-related AEs and UPs and all SAEs (whether or not they are skin product-related) and will be reported according to the timelines specified in the MOOP and the DSMP.

8.1 Definitions

8.1.1 *Adverse Event (AE)*

Any untoward or undesirable, although not necessarily unexpected, event experienced by a human participant that may be a result of:

- The interventions and interactions in the research
- The collection of identifiable private information in the research
- An underlying disease, disorder, or condition of the participant that could be reasonably attributed to emollient use
- Other circumstances unrelated to the research or any underlying disease, disorder, or condition of the participant

8.1.2 *Serious Adverse Event (SAE)*

Any AE that:

- Is fatal
- Is life-threatening
- Is persistent or significantly disabling or incapacitating
- Results in inpatient hospitalization or prolongation of hospitalization
- Results in psychological or emotional harm requiring treatment (not applicable in our population)
- Creates a persistent or significant disability
- Causes a congenital anomaly or birth defect (not applicable in our population)
- Results in a significant medical incident (considered to be a serious study related event because, based upon appropriate medical judgment, it may jeopardize the participant and may require medical or surgical intervention to prevent one of the outcomes listed in this definition)

8.1.3 *Unanticipated Problem (UP)*

Events that are not expected given the nature of the research procedures and the participant population being studied and suggest that the research places participants or others at a greater risk of harm or discomfort related to the research than was previously known or recognized. Harm to a participant need not occur for an event to be an unanticipated problem.

8.1.4 *Deviation*

A deviation is any noncompliance with the clinical study protocol, Good Clinical Practice, or Manual of Operating Procedures requirements. The noncompliance may be on the part of the participant, the investigator, or study staff. As a result of deviations, corrective actions are to be developed by the study staff and implemented promptly.

All deviations will be reported according to the timelines specified in the MOOP and the DSMP.

8.2 Reporting Adverse Events

All AEs, SAEs, and UPs will be documented on the appropriate adverse event questionnaire, entered into the REDCap database, and reported to the DCC as outlined below.

- All skin product-related AEs and all SAEs will be reported by participants in their surveys (at defined contacts) or by direct notification of study staff (through website links or by directly calling study phone number).
- All skin product-related AEs and all SAEs identified during chart audit will be entered into REDCap by PBRN research coordinators.

The DCC will evaluate each event and will determine reporting requirements. The DCC will report events to the Data and Safety Monitoring Board (DSMB) according to the following timeframes:

- All SAEs and UPs that require expedited reporting (SAEs that are deemed related and unexpected, all UPs) will be reported to the IRB within 48 hours of the time the PI learns of the event.
- Only SAEs provided to the study team will be reported.
- All other AEs will be reported to the DSMB semi-annually.
- Summary AE and SAE reports will also be submitted to the IRB at least annually.

9 STUDY OVERSIGHT

In addition to the PI, Clinical Coordinating Center, and Data Coordinating Center having responsibility for oversight, study oversight will be under the direction of a Data and Safety Monitoring Board (DSMB) created with the NIAMS. The DSMB will review reports bi-annually, starting 6 months after the first patient enrolls, to assess safety, study progress, and data integrity for the study. If safety concerns arise, more frequent meetings may be held. The DSMB will operate under the rules of a NIAMS-approved Data and Safety Monitoring Plan (DSMP) with oversight by NCR (formerly KAI) Research, the NIAMS Collaborator. The DSMP will outline the charge to the NIAMS-approved monitoring body and is intended to be a living document to be modified at any time if any processes or procedures were to change.

The PI will routinely report ongoing study activities with emphasis on data integrity and participant safety issues, such as SAEs and other events requiring expedited reporting.

10 STATISTICAL CONSIDERATIONS

10.1 Study Hypotheses

The primary hypothesis of this study is that an intervention to encourage parents to apply daily emollients will reduce the cumulative incidence of AD at two years of age. We will test the hypothesis that the relative risk of AD for the treatment versus control group is not equal to one.

10.2 Study Outcomes

10.2.1 Primary outcome

The primary outcome will be any AD diagnosis made by the child's healthcare provider by 27 months of age (cumulative incidence or cumulative proportion) using standard criteria.⁷⁶ (See Section 2.2)

10.2.2 Key Secondary Endpoints

The key secondary endpoints include: AD diagnosis using parental report, need for prescription anti-inflammatory cream for the skin, incidence of skin care-related adverse events and skin infection, tolerability of the intervention, number and type of yearly wheezing episodes that predict asthma risk⁴¹ and immediate type I hypersensitivity symptoms related to foods. In children who develop AD, the severity of symptoms (POEM) and the impact on infant quality of life (IDQOL) will be measured.^{43,44} The Statistical Analysis Plan contains a full list of secondary outcomes with supporting references.

10.3 Power and sample size calculations

10.3.1 Power and sample size

10.3.2 Primary Outcome

For the purpose of the primary analysis, we will include a sufficient number of babies in a 1:1 ratio for the two study arms to provide an overall type I error rate of 0.05 and 80% power to detect a 30% relative reduction in cumulative incidence over 2 years (also known as

incidence proportion) of AD (RR=0.7). From our planning grant, we estimated the baseline cumulative incidence of AD in this age group and target clinics at 24% at age 2. The trials in high-risk populations of daily vs no emollient have shown reductions of 50%, we assumed a more conservative 30% reduction to 16.8%. Using the O'Brien-Fleming group sequential spending function approach, a total of 982 infants (491 per arm) are required to detect this difference in proportions. Allowing for an approximate 20% loss to follow-up, we plan to enroll **1,250** dyads (625 per arm). Sample size calculations were performed using Stat/IC version 16.1.

Table 6. Power to detect plausible interactions in exploratory analyses (Aim 2).

| Risk factor | AD risk | Prev-alence | Tx effect if RF+ | Tx effect if RF- | Tx effect DIFF | Power at $\alpha = 0.1$ |
|--------------------|---------|-------------|------------------|------------------|----------------|-------------------------|
| Family hx of atopy | 2.0 | 0.50 | 0.63 | 0.83 | -0.20 | 0.48 |
| | | | 0.60 | 0.90 | -0.30 | 0.56 |
| | | | 0.57 | 0.97 | -0.40 | 0.64 |
| High humidity | 0.8 | 0.44 | 0.82 | 0.62 | 0.20 | 0.40 |
| | | | 0.89 | 0.58 | 0.30 | 0.52 |
| | | | 0.95 | 0.54 | 0.40 | 0.65 |
| Cat owner | 1.0 | 0.30 | 0.84 | 0.64 | 0.20 | 0.36 |
| | | | 0.91 | 0.61 | 0.30 | 0.48 |
| | | | 0.98 | 0.58 | 0.40 | 0.60 |
| Dog owner | 0.7 | 0.37 | 0.84 | 0.64 | 0.20 | 0.36 |
| | | | 0.91 | 0.61 | 0.30 | 0.46 |
| | | | 0.98 | 0.58 | 0.40 | 0.59 |

10.3.3 Power and sample size for detecting effect modifications

To determine our power to detect significant effect size differences stratified by various baseline variables (interaction) such as sex, race or ethnicity, atopic family history, climate, and pet ownership, we generated plausible 2x2 tables of risk factors (RFs) and AD for each treatment group that would yield absolute differences in the treatment effect of 0.2, 0.3, and 0.4, taking into consideration the study sample size, overall projected AD and treatment effect, previously published risk of AD for the RF, and prevalence of the RF. We simulated 500 replicates of each scenario using the binomial probabilities from the 2x2 tables and tested for significance of the interaction in a log-binomial (relative risk) model as described below. The power estimates in Table 6 are the proportion of simulated datasets in which the null hypothesis was appropriately rejected.

10.4 Statistical analyses

10.4.1 Analysis of Primary Endpoint

For our primary analysis, we will contrast the risk of diagnosed AD by two years of age for the intervention versus control groups under an intention-to-treat (ITT) assumption, where all subjects will be analyzed according to the group to which they were allocated regardless of adherence or group cross-over, and missing outcome values will be multiply imputed using the expectation-maximization (EM) algorithm.⁷⁸ Model: We will use logistic regression with a treatment variable (intervention=1, control=0) and perform a two-tailed likelihood ratio test of the treatment effect at the overall 0.05 level of significance using an O'Brien-Fleming critical boundary to accommodate one planned interim analysis. Because randomization will have been stratified by clinic and family history of AD in a first-degree relative (yes/no), we will include these variables to avoid overestimation of the p-value.^{79,80} We will estimate the absolute and relative differences between groups as the (1) difference and (2) ratio, respectively, of the average conditional predicted risk for intervention versus controls from the logistic model, calculating standard errors and 95% confidence intervals using the delta method. We will use an inclusive strategy to select variables when imputing the missing outcomes^{77,81} using intervention status and clinic along with parent-reported provider diagnosis, risk factors, and emollient use from electronic survey and text responses, as well as interaction terms found to be significant in Aim 2 (below).

10.4.2 Effect modification of primary endpoint

We will examine potential modification of the intervention effect by sex (consistent with NIH guidelines), race or ethnicity, atopic family history, climate, and pet ownership by creating separate logistic regression models under multiple imputation that include the variable of interest with intervention status and an interaction term, adjusting for stratification variables. Multiple imputation will be performed as above with the interaction term included in the imputation step. We will test for significance of the interaction term with a two-sided Wald test at the 0.1 level. A level of 0.1 was used because of the exploratory nature of this aim that will be solely used to guide future research and due to the impracticality of fully powering this secondary analysis.

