3.6. Analysis Populations

The **Intention-to-Treat (ITT) Population** will contain all randomized participants. Missing outcomes will be multiply imputed to reduce bias without exaggerating precision per recommendations by Little and Yau for longitudinal studies³.

The **Complete Case Population** will include the subset of participants with non-missing primary outcomes.

The **Per-Protocol Population** will assign participants who report emollient use to the intervention arm (regardless of randomization), and those who report no emollient use to the control arm. This dataset will be used to estimate the relationship between frequency of emollient use and AD.

The **Safety Population** includes all randomized participants. Safety outcomes are reviewed regularly by the DSMB.

The **AD Population** includes children with diagnosed AD (chart review).

4. Trial Population

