5.5. Exploratory Subgroup Analyses

In exploratory analyses we will investigate potential differences in treatment effect in subgroups with known or hypothesized risk or protective associations with AD. These are defined in the "Definitions for Subpopulation Analyses" section above.

For each analysis, we will estimate differences in the treatment effect on both the absolute (i.e. risk difference) and relative (i.e. ratio) scales. After calculating the raw differences, we will estimate them based on a model that incorporates the same variables as in other analyses, but with main effects and interactions for the subgroup variables outlined above. Most of these are either binary or continuous; in the case of a multi-level categorical variable, we will use a set of design variables. The analysis addressing ceramides will only use main effects, without interaction terms. The model will use the full ITT dataset with provider-diagnosed AD as the outcome. The p value for the single interaction coefficient (or for the combination of interaction coefficients, if multiple design variables are used) will provide an estimate of statistical significance for a difference in treatment effects in the subgroups being modelled. We plan to use a significance threshold of 0.10 for identifying effects that may warrant further investigation. (Designing the trial for a lower threshold was not feasible.)

More important than p values, we plan to rely on the magnitude of effects to determine whether the intervention is more effective in some subgroups than others. It is difficult to specify a threshold for the magnitude of difference in advance. The planned presentation of results is given in Table 5.

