If $>5\%$ of observations are missing outcomes, then further steps are needed. In addition to the analytic steps described here, we will discuss with members of the study team who interact with participants and clinic staff and may have insight into reasons for loss to follow-up that may or may not be reflected in recorded data. As a first step, we will create an indicator variable $R=1$ if the outcome is missing, $R=0$ if not missing. This variable R can be used to test whether missingness is associated with other variables, particularly:

- Study arm
- Family history of atopy
- Date of enrollment in study
- Parent report of AD
- Child's Eczema Questionnaire (CEQ) signs of AD
- UK Working Party criteria for AD
- PBRN

If differences are found (at $p < 0.10$, approximately, for an inclusive approach) then covariate-dependent missingness at least partly explains the missingness mechanism. Any such variable should be used in the multiple imputation model (or included in the main model without imputation) to produce unbiased estimates.

Multiple imputation will be performed using iterative chained equations over five (5) imputation sets. At the time of writing, the performance of multiple imputation when the model includes a random effect, such as the recruiting clinic in our model, is not well understood, and software to run the model we have proposed under multiple imputation is not readily available. (The estimation command is not available in Stata version 16, for example). Alternatives include (a) substituting a Poisson or logistic model, (b) omitting clinic, which should not be strongly associated with treatment outcome, or (c) Bayesian approaches, which could be especially useful if we suspect that data are missing not at random. The multiple imputation results will be considered the primary findings and will be reported along with complete case analysis.

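### SAP 5.9 does not carry over the protocol's rule that the interaction term goes into the imputation step, so exploratory subgroup differences shrink if outcomes are imputed as the SAP describes

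*Protocol*

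**What the plan says.** Protocol 10.4.2 examines effect modification by sex, race or ethnicity, atopic family history, climate and pet ownership, each in its own model under multiple imputation. The imputation is to be done as for the primary endpoint, but "with the interaction term included in the imputation step". Protocol 10.4.1 also adds to the primary imputation model any interaction found significant in Aim 2.

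SAP 5.9 sets out a different procedure. If more than 5% of outcomes are missing, an indicator of missingness is tested against candidate variables: arm, family history, enrollment date, parent-reported AD, the Children's Eczema Questionnaire, the UK Working Party criteria and PBRN. For those associated at about p<0.10, the rule is: "Any such variable should be used in the multiple imputation model (or included in the main model without imputation) to produce unbiased estimates". The method is given as "Multiple imputation will be performed using iterative chained equations over five (5) imputation sets". No interaction is mentioned. Of the SAP 5.2 subgroup variables, only family history is on the list. Climate, animals, age at randomization, bathing, caesarean birth, sex, race and ethnicity are not.

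SAP 5.5 places the interaction in the analysis model: "The model will use the full ITT dataset with provider-diagnosed AD as the outcome". SAP 5.6 does the same for sex, race and ethnicity. SAP 3.6 says of the intention-to-treat population: "Missing outcomes will be multiply imputed to reduce bias without exaggerating precision". The SAP revision history does not mention the change in imputation model.

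**The concern.** An outcome drawn from a model with no arm-by-subgroup term carries no such interaction on that model's scale, except what other predictors of the outcome bring in. Each imputed child therefore dilutes the interaction that the analysis model then estimates.

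Estimating these interactions is the purpose of Aim 2, and the plan's own power for them is only 0.36 to 0.65 (Protocol Table 6, SAP Table 1). SAP 5.5 says it will give more weight to the size of the subgroup differences than to p values, and size is what is biased. SAP 5.2 adds that a stronger effect in babies with a family history would point to recommending emollient in that group only, so dilution could blur a pattern the aim was written to find.

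**Working it through.** **Inputs.** Control risk 24%, intervention risk 16.8%, 491 per arm, 1,250 enrolled, about 20% loss (SAP 2.3). Family history: prevalence 0.50, AD risk ratio 2.0 (SAP Table 1). Sensitivity and specificity of parent report against the chart diagnosis are assumptions (0.80/0.90 and 0.90/0.95), as the documents give no figure. The imputation model is taken as logistic, and missingness as random and equal across cells.

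**The plan's own figures.** The two-proportion sample size reproduces: 490.5, rounded up to 491 per arm. The interaction powers for family history (0.48, 0.56, 0.64) do not. A two-sided 0.10 Wald test on the log risk-ratio scale gives 0.27, 0.45, 0.64 with 982 children and 0.31, 0.53, 0.73 with 1,250. The documents do not state the number of children simulated. That is a separate matter, and nothing below relies on the table's powers.

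**Step 1, true risks** for the 0.60/0.90 row. Control risks are 0.16 without family history and 0.32 with it (average 0.24). Intervention: 0.16 × 0.90 = 0.144 and 0.32 × 0.60 = 0.192 (average 0.168, as planned). True interaction: ln(0.60/0.90) = −0.405, a ratio of risk ratios of 0.667.

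**Step 2, imputed risks.** A logistic model with arm and family history but no product, fitted to these cells, gives 0.181 and 0.299 (control), 0.123 and 0.213 (intervention).

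**Step 3, mix.** With a share m missing, expected cell risk = (1 − m) × true + m × imputed. At m = 0.20:

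| Cell | True | Imputed | Mixed |
|---|---|---|---|
| Control, no family history | 0.160 | 0.181 | 0.1642 |
| Control, family history | 0.320 | 0.299 | 0.3158 |
| Intervention, no family history | 0.144 | 0.123 | 0.1398 |
| Intervention, family history | 0.192 | 0.213 | 0.1962 |

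Ratio of risk ratios = (0.1962/0.3158) / (0.1398/0.1642) = 0.730; log −0.315. Retained: 0.315/0.405 = 78%.

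**Step 4, shrinkage by missing fraction and auxiliary variable.**

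| Missing | No parent report | 0.80/0.90 | 0.90/0.95 |
|---|---|---|---|
| 5% | 6% | 3% | 2% |
| 10% | 11% | 7% | 4% |
| 20% | 22% | 13% | 8% |
| 30% | 33% | 20% | 11% |

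Across all three family-history rows at 20% missing, shrinkage is 22% to 24% without parent report and 7% to 14% with it.

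**Step 5, the protocol's rule.** With the product term in the imputation model the fitted cell risks equal the true ones, and 100% of the interaction is kept at every missing fraction.

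**Step 6, power.** Two separate simulations used the 0.60/0.90 row, 1,250 children and 20% missing, with 2,000 trials per scenario in one and 1,500 per setting in the other; the first used five imputations and two-sided 0.10. Power with the product term, then without it:
- No parent report: 0.44 to 0.31, and 0.44 to 0.28.
- Parent report 0.80/0.90: 0.47 to 0.39, and 0.45 to 0.39.
- Parent report 0.90/0.95: 0.52 to 0.47.

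**The case against.** A reader might infer that the SAP has removed the protocol's rule. The documents do not support that. No SAP sentence excludes interactions, the candidate list is introduced as particular examples, the approach is described as inclusive, and the SAP names protocol version 13 as its companion. Nor does the SAP say that one imputed dataset serves every analysis. An analyst could follow both documents. What stands is that an analyst working from SAP 5.9 as written is not told to include the term, and would normally take the later and more detailed document as the instruction.

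A reader might also take 22% as the expected shrinkage. That figure applies only when nothing in the imputation model carries outcome information on individual children. Parent-reported AD, the Children's Eczema Questionnaire and the UK Working Party criteria are all candidates, and they bring part of the interaction back. On the other side, SAP 5.9 admits them only if they are associated with missingness, and some children without a chart outcome may also lack surveys. Hence a range.

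The bias is also avoidable within the SAP. With at most 5% missing nothing is imputed, and covariates may go in the main model without imputation. Complete-case results escape this mechanism, but the SAP promises them beside the imputed findings in the context of the primary outcome, and SAP 5.5 does not repeat that promise for interactions. Finally, Protocol 10.4.2 says Aim 2 serves only to guide future research. That limits the importance of the point but does not remove the bias.

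**Conclusion.** The point holds as a gap between the documents with a known direction of bias. At the planned 20% missing, the family-history interaction (0.60 versus 0.90) is shrunk by about 22% without parent-reported AD in the imputation model and by about 8% to 13% with it. The expected ratio of risk ratios is then 0.730, or 0.688 to 0.703, instead of 0.667. Power drops from about 0.44 to about 0.3 without parent report, and by roughly 0.05 to 0.08 with it.

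This rests on missingness at random, logistic imputation and the assumed accuracy of parent report. Under SAP 5.9 a child with a recorded diagnosis is never missing, so real missingness depends on the outcome; that would be a further bias not counted here. The pull is towards no interaction on the imputation model's scale: with a constant risk ratio of 0.70, the ratio of risk ratios moves only to 1.013 at 20% missing.

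The working does not show that the primary result is biased, and no such claim is made. The trigger also needs care: SAP 5.3 speaks of imputing when fewer than 5% are missing, the reverse of SAP 5.9, which is followed here. The point is minor, but worth correcting before analysis.

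**What to change.** Add to SAP 5.9: for each interaction analysis in 5.5 and 5.6, the outcome imputation model always includes arm, the subgroup variable and their product, whether or not these are associated with missingness. Imputing separately by arm, with the subgroup variable in each model, does the same job. Keep parent-reported AD as a predictor in every case. The clause on association matters because, read literally, the present rule would admit even study arm only if it predicted missingness. If the team prefers to depart from Protocol 10.4.2, the SAP should say so and give the reason.

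The cost is one sentence and one extra imputation run per subgroup variable. No new data are needed.
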